Drug Substance	Xuezhikang
Study Number	ESR-21-21279
Version	3.0
Date	2021.11.19

A 24-week, Multi-center, Randomized, Open-Label Clinical Trial to Compare the Impact of Xuezhikang and Atorvastatin on Glucose Metabolism in Dyslipidemia Patients with Prediabetes (XTREME Study)

Principal Investigator: [name]

Co-investigator: [name]

[name]

Leading Hospital: Capital Medical University, Beijing Anzhen Hospital

Sponsor: Ruyang Rural Health Institute(RRHI)

STUDY PROTOCOL SUMMARY

Study Title	A 24-week, Multi-center, Randomized, Open-Label Clinical Trial to Compare the Impact of Xuezhikang and Atorvastatin on Glucose Metabolism in Dyslipidemia Patients with Prediabetes
Objectives	
Primary objective
 
To determine whether XZK 1200mg/d, compared to atorvastatin 20mg/d, has a favorable impact on HbA1c levels from baseline to 24 weeks in dyslipidemia patients with prediabetes.
 
Secondary objective
 
(1) To evaluate the impact of XZK 1200mg/d on fasting plasma glucose (FPG), post prandial glucose (PPG) 2h and insulin production index levels compared with atorvastatin 20mg/d after 24 weeks of treatment in dyslipidemia patients with prediabetes.
 
(2) To evaluate change in LDL-C levels after 24 weeks of treatment with XZK 1200mg/d as assessed by percentage change from baseline.

Study design	This study is a prospective, randomized, open-label, multi-center trial. The primary objective of the study is to assess whether XZK 1200mg/d, compared to atorvastatin 20mg/d, has a favorable impact on HbA1c levels at 24 weeks of treatment in dyslipidemia patients with prediabetes
Treatment / Interventions	
Experimental group: Xuezhikang Capsule, 1200mg / day, twice a day, 2 capsules each time, after meals in the morning and evening.
 
Control group: Atorvastatin Calcium Tablets, 20mg/day, once a day, one tablet each time, before bedtime;
 
Continuous treatment for 24 weeks.

Investigational product	Experimental drug: Xuezhikang Capsule, specification: 300mg / capsule.

	Control drug: Atorvastatin Calcium Tablets, specification: 20mg / tablet.
Study Centre	This study will include approximately 20 sites in China
Number of subjects planned	392 subjects
Planned Study period	Estimated date of the first subject enrolled Jul 2022 Estimated date of the last subject completed Jul 2023
Inclusion Criteria	
(1) Written informed consent provided
 
(2) Age ≥ 40 years
 
(3) Diagnosed Prediabetes, meeting one of the following conditions:
 
 ✓ Impaired fasting glucose (IFG): $5.6 \text{ mmol/L} \leq \text{FPG} < 7.0 \text{ mmol/L}$; ✓ Impaired glucose tolerance (IGT): $7.8 \text{ mmol/L} \leq 2\text{h PPG}$ during 75g OGTT $< 11.0 \text{ mmol/L}$; ✓ HbA1c 5.7-6.4% (39-47 mmol/mol) 
(4) Dyslipidemia meets one of the following conditions:
 
 ✓ Fasting LDL-C $\geq 3.4 \text{ mmol/L}$ and $< 4.9 \text{ mmol/L}$, and $\text{TG} \leq 5.6 \text{ mmol/L}$ ✓ Fasting non-HDL-C $\geq 4.1 \text{ mmol/L}$ and $< 5.7 \text{ mmol/L}$, and $\text{TG} \leq 5.6 \text{ mmol/L}$ 
(5) Completed one-week Patient diary, recorded at least 5 days in a week.

Exclusion criteria	
(1) Patient with proven or documented atherosclerotic cardiovascular disease (ASCVD), including acute coronary syndrome (ACS), history of myocardial infarction (MI), stable or unstable angina pectoris, coronary or other revascularization, ischemic stroke, transient ischemic attack and peripheral vascular disease (PAD), etc.
 
(2) Diagnosed diabetes
 
According to 2021 the American Diabetes Association (ADA) “Standards of

Medical Care in Diabetes”

- ✓ FPG \geq 126 mg/dL (7.0 mmol/L).
 - ✓ 2-h PG \geq 200 mg/dL (11.1 mmol/L) during OGTT.
 - ✓ A1C \geq 6.5% (48 mmol/mol).
 - ✓ In a patient with classic symptoms of hyperglycemia or hyperglycemic crisis, a random plasma glucose \geq 200 mg/dL (11.1 mmol/L).
- (3) Patients with any lipid lowering drugs in the previous 3 months, including but not limited to statins, bile acid sequestrants, cholesterol absorption inhibitors, PCSK9 inhibitors, nicotinic acid, fibric acid derivatives, fibrates, other traditional Chinese medicine and n-3 fatty acids.
- (4) Patients with any antidiabetic drugs.
- (5) Contraindications to XZK or Atorvastatin:
- ✓ Allergic to XZK or Atorvastatin.
 - ✓ Pregnancy or breastfeeding
- (6) Uncontrolled hypertension (systolic blood pressure \geq 180 mm Hg and/ or diastolic blood pressure \geq 110 mm Hg) at screening.
- (7) Active liver disease or hepatic dysfunction, including continuously elevated liver transaminase due to unknown causes. Abnormal liver function test at baseline (ALT or AST $>$ 3 \times ULN).
- (8) Known renal dysfunction or elevated serum creatinine levels at baseline (with an eGFR \leq 60 mL/min/1.73 m²).
- (9) Other endocrine diseases that might influence the levels of lipid or lipoprotein, such as hypothyroidism.
- (10) Patient has participated in clinical trials of other drugs in the past three months.
- (11) Previous statin treatment causes creatine kinase (CK) increased 10 times, or myalgia myopathy (muscle pain or muscle weakness, accompanied by

	
Creatine phosphokinase (CK) exceeds 10 times the ULN)
 
(12)Estimated life expectancy < 6 months at the time of enrollment
 
(13)Abuse of alcohol, or history of alcohol abuse.
 
(14)Close affiliation with the investigators, e.g., a close relative for the investigator, dependent person (e.g., employee or student of the investigators)

Visit plan	5 visits: including enrollment period, baseline period, 4 weeks, 12 weeks and 24 weeks after randomization
Statistical Analyses	
Analyses will be performed by SAS 9.4 statistical software.
 
Descriptive statistics will be calculated, including n, means, standard deviations, medians, and interquartile ranges for continuous variables and frequency counts and percentages for categorical variables.
 
Percentage will be calculated based on non-missing data unless otherwise specified. Data will be examined for skewness, outliers.
 
Transformations will be undertaken as needed.
 
Missing data will be assumed missing completely at random. In general, no imputation will be applied unless otherwise specified. The primary and secondary endpoint will be analyzed using covariance(ANCOVA) model with treatment (XZK, atorvastatin) use the baseline HbA1c as the covariate.

Data collection	Case report form (CRF)

TABLE OF CONTENTS

STUDY PROTOCOL SUMMARY..... 2

TABLE OF CONTENTS 6

LIST OF ABBREVIATIONS AND DEFINITION OF TERMS..... 11

1 INTRODUCTION..... 13

1.1 Background 13

1.2 Rationale for study design 13

1.3 Benefit/risk and ethical assessment 15

1.4 Study Design 17

 1.4.1 Overall design 17

 1.4.2. Randomization 17

 1.4.3. Minimizing Sources of Bias 17

 1.4.4 Number of Centers 17

 1.4.5 Number of Participants..... 17

 1.4.6 Estimated Study Duration 17

 1.4.7 Study Duration for Participants..... 18

 1.4.8 End of Study..... 18

2 STUDY OBJECTIVES 18

2.1 Primary Objective 18

2.2 Secondary Objective 18

2.3 Safety 19

3 STUDY POPULATION 19

3.1 Inclusion Criteria..... 19

3.2 Exclusion Criteria..... 20

3.3 Subject enrolment and randomization 21

3.3.1 Number of Centers	21
3.3.2 Number of Participants.....	21

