1.4.2. Randomization

Randomization of participants that meet all inclusion criteria and do not have any exclusion criteria will be randomly allocated in a 1:1 ratio to XZK group (xuezhikang [1200mg/d]) or ATV group (atorvastatin [20mg/d]) stratified by center and age(≥ 60 years old, < 60 years old) Randomization will be done using a central, automated, web-based electronic randomization software. Randomization will occur within 3 days after the Laboratory result of randomization visit reported .

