4.2.2 Randomization and treatment period (Visit1-Visit4)

Subjects won't be able to eat or drink anything for eight hours before visit 1, visit 2, visit 3 and visit 4.

Visit 1 (Randomization)

1. Before randomization, the investigator should complete the following actions and collect the relevant data:

- Collect general information:

Demographics data: gender, date of birth, education, insurance
- Retrieving and reviewing the Patient Diary
- Collect the information of clinical assessment such as Serum lipids (TG/non HDL-C/TC/LDL-C), HbA1c , Plasma Glucose (PG), PPG, insulin and C-peptide at fasting and 2h after glucose solution (75g glucose) . Hepatic function (Bilirubin, albumin, liver enzymes), Creatine kinase (CK), Renal function (Serum creatinine, BUN ,eGFR), Routine blood test, Pregnancy test (HCG test for women of childbearing potential only),and ECG. According to the results of the above tests, screen the patients again.
- Eligibility criteria: To verify the participants satisfy all the inclusion criteria and without any exclusion criteria.

2. Randomization.

3. Medical history: Including previous medical history, treatment before screening and other comorbidities.

4. Physical examination: blood pressure, pulse rate, weight, height.

5. Collect the information of Concomitant medications.

6. Collect the information of history of adverse events with statins.

7. Collect physical activity information: Physical activity level by for Measurement of a Person's Habitual Physical Activity (IPAQ)

8. Patients should be guided for medication.

9. Distribute study drugs by groups, patients should start the treatment after the day of randomization

Visit 2 (4 weeks after treatment phase)

1. Collect the information of Concomitant medications.
2. Collect the information of adverse events. If any AE is reported, relevant laboratory test should be collected.
3. Collect the information of clinical assessment such as Serum lipids (TG/non HDL-C/TC/LDL-C), Plasma Glucose (PG), PPG, insulin and C-peptide at fasting and 2h after drinking glucose solution (75g glucose) . Hepatic function (Bilirubin, albumin, liver enzymes), Creatine kinase (CK), Renal function (Serum creatinine, BUN ,eGFR).
4. Collect physical activity information: Physical activity level by for Measurement of a Person's Habitual Physical Activity (IPAQ)
5. Patients should be guided for medication and lifestyle
6. Review of the patient's diary, compliance to study medication

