5.1.2 Secondary endpoints

The change value of FBG, PPG 2h and HOMA-IR from baseline to 24 Weeks or before antidiabetic therapy initiation within 24 weeks.

The percentage change of LDL-C levels from baseline to 24 Weeks or before antidiabetic therapy initiation within 24 weeks.

The percentage change of non HDL-C levels from baseline to 24 Weeks or before antidiabetic therapy initiation within 24 weeks.

The change value of HbA1c levels from baseline to 12 Weeks or before antidiabetic therapy initiation within 12 weeks.

The change value of FBG, PPG 2h and HOMA-IR from baseline to 12 Weeks or before antidiabetic therapy initiation within 12 weeks.

The percentage change of LDL-C levels from baseline to 12 weeks or before antidiabetic therapy initiation within 12 weeks.

The percentage change of non HDL-C levels from baseline to 24 Weeks or before antidiabetic therapy initiation within 12 weeks.

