8.4 Efficacy analysis

8.4.1 The primary endpoints

The change value of HbA1c levels from baseline to 24 Weeks or before antidiabetic therapy initiation within 24 weeks will be analyzed using covariance(ANCOVA) model use the treatment group(XZK, atorvastatin) as the group and the baseline HbA1c as the covariate. The results will be presented as least squares means (lsmeans) with 95% confidence intervals and p-values. Model assumptions will be explored and, if necessary, appropriate transformations or non-parametric analysis techniques will be used. The primary analysis set for this analysis is the full analysis set (FAS).

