8.4.2 Secondary endpoints

For each secondary endpoint, an ANCOVA model will be used that is similar to the one described for the primary analysis above.

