8.5 Subgroup analyses

In addition to the analysis described above, a set of analyses will be reported to explore whether intervention effects on the primary and secondary outcomes are consistent across subgroups of interest. These subgroups are:

- a) male vs. female,
- b) senior vs. non-senior (aged ≥ 60 at randomization vs. aged < 60),
- c) BMI $\geq 28\text{kg/m}^2$ vs. BMI $< 28\text{kg/m}^2$

For each subgroup analysis, an ANCOVA model will be used that is similar to the one described for the primary analysis above, but with additional terms identifying subgroup membership and the intervention by subgroup interaction. We will report the Hommel adjusted p-values for the interaction effects.

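### Baseline HbA1c is named as covariate for ten secondary comparisons that are not HbA1c, and the randomisation strata are in no main efficacy model: precision is lost, validity is not

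*Protocol*

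**What the plan says.** - **Secondary model, summary (Statistical Analyses):** "The primary and secondary endpoint will be analyzed using covariance(ANCOVA) model with treatment (XZK, atorvastatin) use the baseline HbA1c as the covariate".
- **Secondary model, section 8.4.2:** "For each secondary endpoint, an ANCOVA model will be used that is similar to the one described for the primary analysis above". No covariate is named.
- **Primary model, section 8.4.1:** the ANCOVA is to "use the treatment group(XZK, atorvastatin) as the group and the baseline HbA1c as the covariate". No other term is listed.
- **Secondary endpoints, section 5.1.2:** among others, "The change value of FBG, PPG 2h and HOMA-IR from baseline to 24 Weeks", and percentage changes in LDL-C and non-HDL-C.
- **Randomisation, section 1.4.2:** 1:1, "stratified by center and age" (60 and over, under 60). About 20 sites are planned (section 1.4.4).
- **Subgroup models, section 8.5:** like the primary model, "but with additional terms identifying subgroup membership and the intervention by subgroup interaction". Age group is one of these subgroups.

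**The concern.** There are two separate points.

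**Covariate.** A change from baseline is usually correlated with its own baseline, so that baseline is the covariate that removes most residual variance. The summary names baseline HbA1c for every secondary endpoint, lipids included. Section 8.4.2 can be read as own-baseline adjustment or as HbA1c again. At stake are precision on ten comparisons and, in an open-label trial, a choice between two models that the text does not close.

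**Strata.** Stratified allocation reduces the true variance of the treatment estimate if centre or age is prognostic. A model without the strata does not credit that reduction. Its standard error is then too large, its intervals too wide and its test conservative, and this includes the primary analysis.

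**Working it through.** **The plan's own figure.** From section 8.1: difference 0.3, SD 1.0, 5% significance, 80% power.

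- Normal approximation, two-sided: n = 2 × 2.8016² × (1.0/0.3)² = 174.4, so 175 per arm. The noncentral t gives 176 (power 80.1%; 79.9% at 175).
- Dropout: 176/0.9 = 195.6, so 196 per arm and 392 in total.

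The plan's numbers reproduce. The calculation is an unadjusted two-group comparison, so neither point changes it.

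**Part 1: counting the endpoints.** At 24 weeks: FBG, 2h PPG, HOMA-IR, LDL-C, non-HDL-C (5). At 12 weeks: the same five plus HbA1c (6), taking the last line of section 5.1.2 as the 12-week non-HDL-C endpoint. Total 11, of which 10 are not HbA1c. The HbA1c endpoints at 12 and 24 weeks already use their own baseline.

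**Part 1: size.** All correlations are assumptions. Let r be the correlation of own baseline with change, and q that of own baseline with baseline HbA1c. If HbA1c relates to the change only through the own baseline, the interval-width ratio (own baseline / HbA1c) is √[(1−r²)/(1−q²r²)]. With q = 0 this is √(1−r²).

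| r | narrower, q = 0 | narrower, q = 0.5 |
|---|---|---|
| 0.2 | 2.0% | 1.5% |
| 0.3 | 4.6% | 3.5% |
| 0.4 | 8.3% | 6.5% |
| 0.5 | 13.4% | 10.6% |
| 0.6 | 20.0% | 16.1% |

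The same can be expressed through the baseline/follow-up correlation ρ, with equal SDs. Residual variance is 1−ρ² with own baseline and (1−ρ)²(1−q²) + 1−ρ² with HbA1c. For ρ from 0.3 to 0.8 and q from 0 to 0.5, the variance ratio runs from 0.65 to 0.92. Intervals are then 19% to 4% narrower (√0.650 = 0.806; √0.923 = 0.961).

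Cases with little gain (q = 0):

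- Eligibility restricts the baseline to SD 0.7 of the follow-up SD. Then r = (ρ−0.7)/√(1+0.49−1.4ρ). At ρ = 0.5, r = −0.2/√0.79 = −0.225, a gain of 2.6%. At ρ = 0.7, r = 0 and there is no gain.
- LDL-C percentage change, baseline cut to 3.4–4.9 mmol/L (assumed true mean 3.8, between-patient SD 0.6, within-patient SD 0.3–0.5, mean fall 32%): r from −0.10 to −0.17, a gain of 0.5–1.5%.

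**Part 2: size.** Simulation of 20,000 trials per row: 352 analysed, 20 centres × 2 age groups, permuted blocks of 4 (assumed), baseline HbA1c in both models. R² is the share of variance explained by the strata beyond baseline HbA1c. Power is at a difference of 0.3 with residual SD 1.0.

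| R² | model SE / true SE, no strata | type I error, no strata | interval width, with / without strata | power without / with strata |
|---|---|---|---|---|
| 0 | 1.005 | 4.9% | 1.003 | 80.0 / 79.8% |
| 5% | 1.020 | 4.4% | 0.979 | 80.3 / 81.5% |
| 10% | 1.041 | 4.1% | 0.953 | 81.6 / 83.9% |
| 15% | 1.077 | 3.6% | 0.927 | 82.2 / 86.1% |

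A second simulation (4,000 trials per setting) gave mean estimates without strata of −0.299 to −0.301 for a true −0.30, so no bias. At R² = 20%, type I error without strata was 3.0%.

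**Cost in degrees of freedom.** 352 − 3 = 349 without strata. Removing 19 for centre and 1 for age leaves 329. The t critical value is 1.967 in both cases.

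**The case against.** **The strata point is a preference.** No passage contradicts another: one describes allocation, another a model. The model without strata is valid and slightly conservative, the planned power is kept, and nothing in the documents shows that centre or age predicts HbA1c change. This is fair as to validity, and the concern claims no invalid inference. But section 8.4.1 spells out a model, so this is a stated choice that can be improved at almost no cost, not a detail left to a SAP. The section 8.5 wording is generic across three subgroup factors and supports the reading only for age; section 8.4.1 suffices alone.

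**The covariate point is loose wording in a synopsis.** The ordinary reading of section 8.4.2 is own baseline. That may be the intent, but the summary affirmatively says HbA1c. A SAP naming own baselines would contradict it, so the text needs correcting either way.

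**The 2–20% range compares with no covariate, while the criticised model already adjusts for HbA1c.** This stands: with q = 0.5 the range is about 1.5–16%. The direction and the remedy do not change.

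**Absence of bias is not unconditional.** This also stands. It holds on average over randomisation with complete data or data missing completely at random. Given a chance imbalance in an endpoint's own baseline, an estimate not adjusted for it is conditionally biased. At 176 per arm, one standard deviation of such imbalance is √(2/176) = 0.107 baseline SDs. Section 8.2 also allows missing at random; missingness that depends on centre or age could bias an analysis that omits them. Both caveats favour the change.

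**Conclusion.** The concern holds. The summary fixes baseline HbA1c as covariate for ten comparisons where the endpoint's own baseline is the natural choice, and section 8.4.2 leaves a second reading open. The main efficacy models omit both stratification factors. The consequence is lost precision, not error: the planned 80% power is not endangered and type I error is not inflated.

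The size depends wholly on assumed correlations and strata R². For the covariate it runs from nothing (restricted baselines) to about 16–20% of interval width. HOMA-IR has no eligibility limit, so a material gain is possible there; for LDL-C percentage change the gain is probably 0.5–1.5%. For the strata, intervals are 2–7% narrower at R² of 5–15%, and 0.3% wider if the strata are not prognostic. The point should be corrected, but it does not threaten the primary conclusion.

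**What to change.** In the summary and in sections 8.4.1 and 8.4.2, state that each ANCOVA contains treatment, the baseline value of the variable analysed, age stratum (60 and over, under 60) and centre. Baseline HbA1c is then the covariate for the HbA1c endpoints only. The handling of small centres can be left to the SAP.

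The cost is protocol wording and about 20 degrees of freedom. No new data are needed: section 4.2.2 already collects the glucose, insulin and lipid baselines at visit 1, and centre and age are known at randomisation.

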1 INTRODUCTION

1.1 Background

Atherosclerotic cardiovascular disease (ASCVD) is the leading cause of death and accounts for 41% of all cause death in China[1]. Management of dyslipidemia is the main strategy to reduce the risk of ASCVD. To lower lipids, statins should be the first-line treatment in clinical practice. However, patients on statin treatment have been shown to exhibit an increased risk of dys-glycaemia and development of type 2 diabetes mellitus (T2DM)[2].

Dyslipidemia and diabetes mellitus are major risk factors of ASCVD, and the prevalence has been reached 40.4%[3] and 10.9%[4] among Chinese adults. China has the largest number of diabetes mellitus with 109.6 million Chinese adults suffering from the disease[5]. Genetic susceptibility may play an important role as Asians have a 60% increased risk of diabetes compared with Caucasians after adjusting for age, sex, and BMI[6].

Therefore, the management of patients with dyslipidemia in Prediabetes poses a challenging dilemma that requires balancing the benefit of reducing serum cholesterol against the risk of dys-glycaemia and development of T2DM, especially for Chinese even Asians.

Xuezhikang (XZK), a traditional Chinese medicine that contains natural lovastatin and multiple components for hyperlipidemia treatment, may have a lower risk of incident diabetes compared with the statin cohort. However, limited information was available to demonstrate XZK does not adversely affect glucose metabolism or incident diabetes. Therefore, we hypothesize that XZK 1200mg/d, compared to atorvastatin 20mg/d, has a favorable impact on the HbA1c levels in dyslipidemia patients with Prediabetes .

The Xtreme study is a 24-week, multi-center, randomized, open-label clinical trial that will compare the impact of XZK and Atorvastatin on glucose metabolism in dyslipidemia patients with Prediabetes. Prediabetes, including impaired fasting glucose (IFG), impaired glucose tolerance (IGT), or A1C 5.7–6.4% . Recruitment will occur at approximately 20 centers, where 392 adult participants in Prediabetes with dyslipidemia will be randomly assigned to receive XZK 1200mg/d or Atorvastatin 20mg/d. Randomized participants will be followed to a common study period.

1.2 Rationale for study design

Up to now, there is no published RCTs to compare the impact of XZK and statins on glucose metabolism in Prediabetes with dyslipidemia. However, systematic reviews of several large observational studies have recently

found statin treatment is associated with a modest increase in HbA1c in patients with T2DM. In these patients, the mean difference of HbA1c increased by 0.17% (95% CI 0.07, 0.27) compared with the blanking control group[7]. For instance, Atorvastatin 20mg is widely used medium intensity statin in clinical practice, but a cohort study based on a database of Korea populations reported that the use of low dose Atorvastatin 10-20mg tended to be a risk factor for onset diabetes (NODM) in Asians[8]. Meanwhile, a small RCT reported that HbA1c level was increased from 6.1% to 6.5% after Atorvastatin 20mg/d treatment for 2 months[9]. The long-term administration of statins might increase the risk of NODM approximately 10%-12%[10]. In short, a diabetogenic role of statins has been demonstrated both from randomized trials and meta-analyses, and risk factors include high dose, prolonged exposure, old age, prediabetic state and metabolic syndrome[11, 12]. In consideration of prediabetes, including IFG, IGT, or A1C 5.7–6.4%, will be further increased the risk of development diabetes mellitus, and the prevalence was 35.7% in China, we choose the patients in Prediabetes with dyslipidemia in our study[4].

XZK, a partially purified red yeast rice (RYR) under controlled pharmaceutical manufacturing conditions, contains a family of naturally occurring statins (monacolins)-most prominently monacolin K, which is identical to the lipid-lowering therapy lovastatin (Mevacor)[13]. In a meta-analysis, after compared the XZK treatment group showed significant lowering LDL-C effect compared with basic therapy groups. [14] Xuezhikang in the China Coronary Secondary Prevention Study trial(CCSPS) has shown that XZK significantly reduced the levels of TC, TG and LDL-C and increased that of HDL-C in patients with hyperlipidemia after 1200mg/d treatment for 8 weeks, among which TC decreased by 23.0%[15]. Furthermore, a retrospective cohort study that used Taiwan's National Health Insurance data on 34,504 persons with a RYR prescription in 2010-2014, found that a lower risk of incident diabetes when compared to lovastatin cohort (HR:0.46, 95% CI 0.43-0.50)[16]. Why XZK can lower the risk of incident diabetes compared to other statins? A variety of mechanisms have been elucidated. As main components in XZK, n-3 polyunsaturated fatty acid (PUFAs) can regulate the activity of key transcription factors to regulate gene expression in lipid metabolism and improve insulin sensitivity of type 2 diabetes mellitus to prevent diabetic complications. Six weeks of supplementation with n-3 PUFAs reduced the postprandial decrease in macrovascular function and meanwhile improved postprandial microvascular function[17]. Moreover, it was reported that magnesium deficiency can lead to the reduction of insulin sensitivity and affect the stability of glucose metabolism. Thus, increasing the intake of magnesium plays an important role in the prevention of noninsulin-dependent diabetes mellitus and its complications. Moreover, selenium reduces the production of oxygen free radicals in the body by glutathione peroxidase to prevent further oxidative damage in the body and the insulin A, B between the two peptide chains for ensuring the complete molecule structure and function of insulin to play a role

in lowering blood glucose. In addition, selenium also has inhibitory effects on complications of diabetes such as osteoporosis and retinopathy.

In addition, XZK has been proved to contain multiple active ingredients which leads to unique MOA and multiple benefits[13]. It is composed of 13 kinds of natural statins, unsaturated fatty acids, ergosterol, amino acids, flavonoids, alkaloid, trace elements, and other substances, and thus could be regarded as a natural lipid lowering polypill[14]. All the above-mentioned components might be involved in the mechanism of XZK to multiple benefits such as antiatherosclerosis, liver protection, anticancer, neural regulation and protection, and kidney protection effects[13]. Previous animal and cell experiments have shown that XZK can also activate the PPAR α pathway and up-regulate apolipoprotein A5 (apolipoprotein A5 is the key regulator of TG metabolism) to achieve higher TG reduction when it reduces LDL-C by the same extent as simvastatin[18]. It is speculated that non-statin elements within XZK may play a synergistic role in regulating blood lipids and inhibiting the synthesis of triglycerides. The China Coronary Secondary Prevention Study (CCSPS) and other clinical studies confirmed that XZK capsules reduce lipid and significantly reduce the overall mortality of patients with coronary heart disease, the incidence of cardiovascular events. According to Chinese guidelines for the management of dyslipidemia in adults of 2016 revision, XZK amongst other statins are recommended for the first-line treatment of cholesterol controlling. Meanwhile, XZK 1200mg/d and Atorvastatin 20mg/d are medium intensity statins recommended in guideline[3]. therefore, we choose Atorvastatin 20mg/d as control drug in our research.

Physicians faced with a dyslipidemia patient with prediabetes often use statins therapy due to perceived efficacy. However, XZK is a promising option in this patient group due to their significantly lower risk of dys-glycaemia without compromising efficacy for lowering lipids in hyperlipidemia. Establishing comparable recurrent NODM rates in individuals with previous Prediabetes state would result in superior DM prevention for these patients.

